#### 9.6.2. Analysis of Study Conduct and Study Discontinuation

An adapted CONSORT diagram will be provided for documenting the number of patients at each reporting schedule. It will also present the patients' situation with regards to their participation in the registry and, if relevant, the reason why and when they stopped to participate.

The total number of patients selected from the registries as well as the number and percentage of patients will also be presented by country and center.

Patient disposition will be summarized and defined as patients who receive ide-cel and are reported to the corresponding registries with either ongoing follow-up, completed follow-up at 15 years or discontinued post-infusion follow-up due to death.

#### 9.6.3. Baseline and Demographic Characteristics

Patients are included into the registry from 2 weeks prior to the ide-cel infusion to any time afterwards. Baseline data are retrospectively reported by data managers after the administration of ide-cel and are collected only once. All information, including any medical history and measurements done prior to the administration of ide-cel, becomes available in the registry as baseline data.

The baseline data will be summarized using descriptive statistics. Individual patient listings will also be provided to support the summary tables. The number and percentage of patients in each of the categories, as listed in Section 9.3, will also be given.

The following baseline data will be presented:

- **Demographics:** Demographic information collected at baseline will be presented using descriptive statistics.
- **Disease History/Comorbidities**: The frequency of patients with at least one comorbidity, as well as frequency counts of different comorbidities will be presented. The ECOG Performance Status score and disease status at infusion will be summarized by frequency counts.
- **Prior Therapy/Prior Medications**: Number of lines of prior therapies will be presented using descriptive statistics. Number of lines of prior therapies will be described as frequency counts. A frequency tabulation of the number of patients with the different types of prior therapies will be given. Also, a frequency tabulation of whether the patient had prior hematopoietic cell transplantations (HCTs) and the types of prior HCTs will be given.
- Lymphodepleting Treatment: A frequency tabulation of the list of lymphodepleting agents will be given.

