### 9.2. Setting

This noninterventional cohort study will be based on secondary data that are collected from existing independent registries, such as the EBMT and the CIBMTR. Both registries use electronic Registry Case Report Forms (CRFs) forms onto which data may be entered directly by the treating centers.

All patients included in the EBMT and the CIBMTR registries are treated by their physicians according to real-world clinical practice. Physicians are trained to identify and approach patients treated with at least one dose of ide-cel to obtain their written informed consent according to the registries' standard procedures, to transfer the data to the EBMT or the CIBMTR and to be shared with competent health authorities, MAH and other parties in line with the signed informed consent forms.

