#### 9.3. Variables

The following variables will be recorded and used within this study:

Classification	Category	Variable	Description
		Patient Code / ID	Unique de-identified ID for patient
		Reporting Center (RC) Name / ID	Center name or ID reporting to the registry
Baseline (at infusion date)	General Identifiers	Manufacturing Site (MFS) Name /ID	Site name or ID producing the CAR T product
(at infusion date)		Apheresis Center (AC) Name / ID	Center name or ID conducting leukapheresis
		Site of Care (SC) Name / ID	Center name or ID treating patient and infusing the CAR T product
		Product Name	Name of CAR T product
Baseline	Product Information	Product Code / ID (Join ID)	Product ID for the first product
		Product Quality: OOS	Product: out of specification, yes/no
	Key Treatment Processes and Timing	Patient Registering Date	Date patient was registered into the registry DB by the RC
		Leukapheresis Date	Date blood was collected at the AC
		Blood Shipment Date	Date blood was shipped from the AC to the MFS
		Blood Arrival Date	Date blood arrived at the MFS
		Manufacturing Start Date	Date MFS started production of CAR T
		Manufacturing End Date	Date MFS completed production of CAR T
		Product Shipment Date	Date CAR T was shipped to the SC
Baseline		Product Receipt Date	Date CAR T arrived at the SC
		Lymphodepleting Therapy Date	Date when lymphodepleting therapy started at SC
		Infusion Date	Date when CAR T was infused to the patient at the SC
		Product Infusion Count	Infusion counting number and total number of infusions
		Diagnosis Date	Date when primary disease was diagnosed
		Last Contact Date	Date when patient was last time in contact with the SC
		Safety Assessment Date	Date of any safety assessments findings (as listed in the safety section below)
		Effectiveness Assessment Date	Date of any effectiveness assessments findings (as listed in the effectiveness section below)

Confidential and Proprietary

Table 4: Variables (Con	tinued)
-------------------------	---------

Classification Category		Variable	Description
		Age	Age at infusion (years)
		Weight	Body weight at infusion (kg)
Deseline	Democratica	Height	Body height at infusion (cm)
Baseline	Demographics	Gender	Gender of patient
		Country	Country of the infusion center
		Region	Region of treatment: North America/Europe/Japan/Rest of the World
		Karnofsky Performance Score	Karnofsky performance score at infusion

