#### 9.6.4. Effectiveness Analysis

#### 9.6.4.1. Analysis of the Secondary Effectiveness Endpoints

- **Overall Survival (OS)**: Overall survival is defined as the time from the date of first infusion to the date of death due to any cause. All patients will be followed for survival information, regardless of whether they receive additional treatment post-infusion. Patients who are alive at last contact date will be censored at that time, but no censoring will be done for additional treatment.
- **Progression-Free Survival (PFS)**: PFS is defined as the time from the date of first idecel infusion to the date of event defined as the first documented relapse or progression or death due to any cause, whatever happens first. Patients who are alive at last contact date will be censored at that time, but no censoring will be done for additional treatment.
- **Time To Event (TTE) Analysis:** Kaplan-Meier estimates and the associated 95% CIs of the median, 25th and 75th percentile will be presented. The two-sided 95% CIs will be computed using the log-log transformation. The survivor function will be displayed graphically using a KM curve.

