## **10. PROTECTION OF HUMAN SUBJECTS**

Data will only be part of the PASS if the patients (and parental/legal representative, when applicable) have given their voluntarily informed consent according to the registries' standard procedures, to allow data to be provided to the EBMT or the CIBMTR and to be shared with competent health authorities, MAH and other parties in line with the signed informed consent forms.

The informed consent form (ICF) used to consent patients will be based upon the ICF templates of the EBMT and/or the CIBMTR, updated in line with the treatment center's standard practices/regulations to fulfil data protection and/or national requirements for informed consent.

In accordance with local regulations, this study will complete all required regulatory and ethical review requirements.

Given that this is an observational PASS, it does not give rise to additional risks for the safety of the patients.

In case a patient treated with ide-cel in the postmarketing setting develops a secondary malignancy of suspected T cell origin, a separate ICF will be used for tumor tissue sample collection and ide-cel transgene testing outside the scope of this PASS.

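### Consent and registration can come at any time after infusion, but OS and PFS run from infusion by Kaplan-Meier with no entry rule, so survival is overstated to the extent that consent is late

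*Protocol*

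**What the plan says.** Four parts of the Protocol bear on this.

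- **Entry (9.6.3).** "Patients are included into the registry from 2 weeks prior to the ide-cel infusion to any time afterwards". No maximum lag is given here or elsewhere.
- **Consent (9.2 and 10).** "Physicians are trained to identify and approach patients treated with at least one dose of ide-cel to obtain their written informed consent". Consent is a condition of inclusion: "Data will only be part of the PASS if the patients (and parental/legal representative, when applicable) have given their voluntarily informed consent". No exception is stated for patients who die before they are asked.
- **Estimation (9.6.4.1).** "Overall survival is defined as the time from the date of first infusion to the date of death due to any cause". Likewise, "PFS is defined as the time from the date of first idecel infusion to the date of event". Patients alive at last contact are censored then. The estimator is named: "Kaplan-Meier estimates and the associated 95% CIs of the median, 25th and 75th percentile will be presented". There is no rule for entry into the risk set.
- **Data (9.3, Table 4).** A Patient Registering Date is listed: "Date patient was registered into the registry DB by the RC". No consent date is listed.

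Section 9.8 discusses missing data, refusal of consent, attrition and poor capture of mortality, and plans to reconcile shipped products with reported patients. It does not mention survival up to consent or registration.

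**The concern.** If a patient can be included only when alive to consent, and consent comes after infusion, the interval between the two is time in which that patient could not have been observed to die. Ordinary Kaplan-Meier from infusion counts the patient as at risk throughout it. Those who died in the same interval without being asked are absent from both numerator and denominator. This is left truncation, and it pushes estimated survival upward.

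For OS the direction follows from the design. For PFS the effect runs only through death: a late registrant is guaranteed alive, not progression-free.

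The unseen patients are early deaths, which matter in a post-authorization safety study. A sample of 1000 does not help, because more patients narrow the interval around a biased value.

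**Working it through.** The protocol gives no figure for OS, for the share consented late, or for the lag, so there is no stated result on this point to reproduce. Its one numerical justification, Table 5, concerns adverse-event precision. Its intervals do reproduce (35/1000 gives 0.0245 to 0.0483), but they have no bearing here.

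**Assumed inputs.** Exponential OS with median m months, so λ = ln 2 / m and S(t) = exp(−λt). A share s of treated patients is consented at a lag L, uniform over 0 to M months and independent of prognosis. The rest are included from infusion. Late patients are included only if alive at L.

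**Formulas.**

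- Fraction of the late group who survive to inclusion: q = (1 − S(M)) / (λM).
- Fraction of all treated patients who die unseen: s(1 − q).
- What ordinary Kaplan-Meier from infusion estimates: S_obs(t) = [(1 − s)S(t) + s·A(t)] / [1 − s(1 − q)]. Here A(t) = (t/M)S(t) + (S(t) − S(M))/(λM) for t ≤ M, and A(t) = S(t) for t > M.

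**Example A: m = 20, s = 0.20, M = 12.** λ = 0.03466, λM = 0.4159, S(12) = 0.6598.

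- q = 0.3402/0.4159 = 0.818, so 0.20 × 0.182 = 3.6% die unseen.
- S_obs(12) = 0.6598/0.9636 = 68.5%, against a true 66.0%.
- The apparent median solves S(t) = 0.5 × 0.9636 = 0.4818, so t = 0.7302/0.03466 = 21.1 months, against 20.

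**Example B: m = 20, s = 0.30, M = 24.** λM = 0.8318, S(24) = 0.4353.

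- q = 0.5647/0.8318 = 0.679, so 0.30 × 0.321 = 9.6% die unseen.
- A(12) = 0.5 × 0.6598 + (0.6598 − 0.4353)/0.8318 = 0.5998.
- S_obs(12) = (0.7 × 0.6598 + 0.3 × 0.5998)/0.9037 = 71.0%, against 66.0%.
- The apparent median is 22.9 months, against 20.

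**Range over m = 15 to 25, s = 10% to 30%, M = 12 or 24.**

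| Case | True 12-month OS | Ordinary KM | Overstatement |
|---|---|---|---|
| m = 25, s = 0.10, M = 12 (smallest) | 71.7% | 72.8% | 1.1 points |
| m = 15, s = 0.30, M = 24 (largest) | 57.4% | 62.9% | 5.5 points |

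**Simulation with wider assumptions.** This used 400,000 patients per scenario, medians of 12, 18 and 24 months, 10% to 50% late, lags up to 12, 24 or 36 months, and administrative censoring at 60 months. Ordinary Kaplan-Meier overstated 12-month survival by about 1 to 10.5 points. With median 18, 25% late and lags up to 24 months, it gave a median of 20.3 months and 12-month survival of 67.2%, against true values of 18.0 and 63.0%. Delayed entry gave 18.0 and 63.0%, and across all scenarios it recovered the true median to within about 0.1 month.

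**Scale against sampling error.** At N = 1000 and 66% survival, before censoring, the 95% half-width is 1.96 × √(0.66 × 0.34/1000) = 2.9 points. Example A's 2.5 points falls just inside it; Example B's 5.0 points does not.

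**The case against.** The strongest reply has four parts.

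1. **The protocol nowhere says that a patient must be alive at registration.** Section 9.6.3 concerns inclusion in the registry and adds that baseline data are reported retrospectively. The registering date is when the center entered the patient in the database. Someone consented around infusion and entered late, even after death, brings no guaranteed-survival time. This stands. A reader might infer that every late registrant is affected, and the text does not support that. What remains is that section 9.2 makes consent after treatment an expected route and section 10 makes consent a condition of inclusion.
2. **The risk-set rule may be left to the SAP.** Infusion is the right origin even under delayed entry, and delayed-entry Kaplan-Meier is still Kaplan-Meier. This stands in part. But section 9.6.4.1 itself fixes origin, censoring and estimator, and an SAP that followed it as written would apply the ordinary method.
3. **The size is invented.** All inputs are assumptions, and the calculation admits only patients alive at consent, so the bias is built in. This stands for the size, not for the direction.
4. **Section 9.8 already deals with selection.** Asking every treated patient does not reach those who die first. Reconciling shipments can reveal under-capture but does not correct the risk set.

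Two stronger readings should be set aside. A reader might infer that incidence rates and cumulative incidence are also counted from infusion without adjustment, but section 9.6.5.1 defers their time periods and methods to the SAP. A reader might also suppose that an event such as a second malignancy prompts registration and distorts that rate; nothing in the document says so.

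**Conclusion.** The point holds for OS, and for PFS through its death component. Sections 9.2, 9.6.3 and 10 together let inclusion depend on survival to a date after infusion, and the analysis in 9.6.4.1 ignores that date. The bias is upward wherever consent is late.

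The 1 to 5.5 points at 12 months rests on exponential survival, a lag unrelated to prognosis, medians of 15 to 25 months and 10% to 30% late. The effect is negligible if few patients are late or if most consent around infusion. PFS was not quantified. No conclusion is drawn about incidence rates or cumulative incidence.

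**What to change.** In 9.6.4.1:

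- Keep first infusion as the time origin and add a delayed-entry (left-truncated) Kaplan-Meier analysis of OS and PFS. Patients whose inclusion required being alive at a later date enter the risk set at that date.
- Use the consent date where the registry can supply it; otherwise use the Patient Registering Date as a proxy and label it as such.
- Do not drop patients whose record was created after death; dropping them would delete early deaths. Define entry by the route of consent rather than by whether the patient later died. Keeping those deaths from infusion while delaying comparable survivors would err downward.
- State how progression documented before entry is handled in PFS.

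In reporting:

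- Tabulate the infusion-to-registration lag, which also shows whether the problem is material.
- Show the acute-event percentages (CRS, neurotoxicity, TLS) for all patients and additionally by early versus late registration, without restricting the main set.
- Report the number infused but never registered, from the shipment reconciliation planned in 9.8.

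The cost is a short protocol edit and SAP programming. The registering date is already collected; a consent date would have to be requested, since Table 4 does not list one. The delayed-entry analysis will have fewer patients at risk in the first months, so its early estimates will be less precise.

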#### 9.6.4. Effectiveness Analysis

#### 9.6.4.1. Analysis of the Secondary Effectiveness Endpoints

- **Overall Survival (OS)**: Overall survival is defined as the time from the date of first infusion to the date of death due to any cause. All patients will be followed for survival information, regardless of whether they receive additional treatment post-infusion. Patients who are alive at last contact date will be censored at that time, but no censoring will be done for additional treatment.
- **Progression-Free Survival (PFS)**: PFS is defined as the time from the date of first idecel infusion to the date of event defined as the first documented relapse or progression or death due to any cause, whatever happens first. Patients who are alive at last contact date will be censored at that time, but no censoring will be done for additional treatment.
- **Time To Event (TTE) Analysis:** Kaplan-Meier estimates and the associated 95% CIs of the median, 25th and 75th percentile will be presented. The two-sided 95% CIs will be computed using the log-log transformation. The survivor function will be displayed graphically using a KM curve.

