#### Table 4:Variables (Continued)

Confidential and Proprietary

Classification	Category	Variable	Description
	Effectiveness	Best Overall Response 1: Biochemical Assessment	Assessment of response based on biochemical assessment
		Best Overall Response 2: Bone Marrow Assessment	Assessment of response based on bone marrow assessment
		Relapse and Progression 1	Outcome of relapse or progression detected by bone marrow and/or biochemical/radiologic assessment
Outcome		Relapse and Progression 2: Therapy	Therapy given for treatment of relapse or progression
		Progression Status	Status of progression
		Relapse Status	Status of relapse
		Cause of Death	Primary cause of death and contributing causes of death #1 to #4
		Survival Status	Survival status at last contact

AC = apheresis center, AE = adverse event, ASTCT = American Society for Transplantation and Cellular Therapy, B2M = beta 2 microglobulin, CAR T = chimeric antigen receptor T cell, CRS = cytokine release syndrome, CT = cell therapy, Cytogen. = cytogenetic, d = day, DB = database, ECOG = Eastern Cooperative Oncology Group, FISH = fluorescence in situ hybridization, FU = follow-up, GVHD = graft-versus-host disease, HCT = hematopoietic cell transplantations, ID = Identifier, Intraven. = intravenous, LD = lymphodepleting, MFS = manufacturing site, NT = neurotoxicity, OOS = out of specification, RC = reporting center, SC = site of care, SM = secondary malignancies, TLS = tumor lysis syndrome.

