## 9.8. Limitations of the Research Methods

As this is an observational PASS based upon secondary use of data, sporadic missing data are inevitable, because certain variables may not have been routinely recorded in the patient medical charts. Furthermore, data will also be missing due to gaps in the follow-up (as routine scheduled visits cannot be mandated in an observational study), and loss to follow-up, especially in this study with a planned duration of 15 years. Details of how missing data are handled are also outlined in the SAP.

The above-mentioned potential issue can lead to significant biasing effects on time to event analyses as well as analyses quantifying a duration. In the EBMT and the CIBMTR registries, data are recorded at baseline, 100 days, 6 months and then yearly. Thus, owing to center specific different levels of compliance, a high variability in the recording of assessment dates is to be expected.

To minimize selection bias, sites are requested to ask every patient treated with ide-cel to share data with the registry. Nevertheless, not all patients will consent to have their data sent to the

Confidential and Proprietary

EBMT or the CIBMTR registries, possibly resulting in a biased sample of patients. A high rate of attrition (particularly if mortality is not captured well) could bias the results. In addition, in order to monitor the reporting, the study team will reconcile shipped products to each center participating in the study with the subsequent compliance of the patient and center with the study.

Additionally, as with every observational study, there will be unmeasured factors that can confound safety and effectiveness analyses. This PASS will attempt to collect accurate and complete data on all known critical confounders; however, residual confounding is always a possibility in any observational study analysis.

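### The PFS censoring sentence repeats the OS rule: it contradicts the PFS event definition for progressed survivors and censors at last contact instead of the last disease assessment

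*Protocol*

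**What the plan says.** Section 9.6.4.1 of the protocol sets out OS and PFS in adjacent bullets.

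- OS: "Overall survival is defined as the time from the date of first infusion to the date of death due to any cause". Censoring: "Patients who are alive at last contact date will be censored at that time, but no censoring will be done for additional treatment".
- PFS: time from first infusion to an event, worded together with its censoring as "first documented relapse or progression or death due to any cause, whatever happens first. Patients who are alive at last contact date will be censored". The full censoring sentence is the same as for OS, word for word.

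The PFS bullet does not limit censoring to patients without relapse or progression, and it does not mention disease assessment.

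The variables table in section 9.3 (Table 4) keeps two dates apart. Last Contact Date is the "Date when patient was last time in contact with the SC", where SC is the site of care. Effectiveness Assessment Date is the "Date of any effectiveness assessments findings". The relapse and progression variable is described as "Outcome of relapse or progression detected by bone marrow and/or biochemical/radiologic assessment".

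Section 9.8 says that "data will also be missing due to gaps in the follow-up", gives the recording schedule as baseline, 100 days, 6 months and then yearly, and warns of bias in time-to-event analyses. It leaves missing-data handling to the SAP. No other section qualifies the PFS censoring sentence.

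**The concern.** The sentence suits OS, because a patient alive at last contact has not had the event. For PFS it fails in two ways.

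1. **Contradiction.** A patient who progresses at month 6 and is alive at month 20 has an event at month 6 under the definition, and is censored at month 20 under the next sentence.
2. **Wrong date.** Suppose the rule is meant for patients alive and progression-free. Progression status is still known only up to the last disease assessment. Contact with the site does not establish it. Time between the last assessment and last contact is credited as progression-free.

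Both errors lengthen PFS. The second matters most where disease assessment stops but contact continues. This is more than detail left to the SAP: the protocol states an explicit rule. An SAP that follows it inherits the conflict, and one that departs from it contradicts the protocol.

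**Working it through.** The protocol gives no PFS target or precision figure, so there is nothing of its own to reproduce. The check compares the wording and then sizes the effect.

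**Wording, by patient state at last contact**

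| State | Event definition | Censoring sentence |
|---|---|---|
| Dead | Event | Silent |
| Alive, no progression | No event | Censored at last contact |
| Alive, progressed | Event at progression | Censored at last contact |

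The third row is the contradiction.

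**Inputs.** From the protocol: median PFS 8.6 months (MM-001, section 7.2.3), used only as an illustration. Assumed, because the documents do not give them: exponential times; independent progression and death; OS median 20 months (range 15–25); the share q of patients who stop assessment while staying in contact, 10–30%; and the last-contact distributions below.

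Monthly rates: λT = ln 2/8.6 = 0.0806 (first event); λD = ln 2/20 = 0.0347 (death); λP = λT − λD = 0.0459 (progression). C is the time of last contact.

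**A. Literal rule.** A progression counts only if the patient has died by C.

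- Counted-event density: e(t) = e^(−λT·t) · {λD·P(C≥t) + λP·E[(1 − e^(−λD(C−t))); C≥t]}
- At risk: R(t) = ∫ₜ^∞ e(u)du + E[e^(−λD·C); C≥t]
- The Kaplan-Meier median m solves ∫₀^m e(t)/R(t) dt = ln 2.
- Share of patients whose progression is wrongly censored: E[e^(−λD·C)] − E[e^(−λT·C)]. For C uniform on 0–60 months this is (1 − e^(−2.079))/2.079 − (1 − e^(−4.836))/4.836 = 0.421 − 0.205 = 0.216.

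| Last contact (months, uniform) | Median PFS, OS 15 / 20 / 25 | Wrongly censored |
|---|---|---|
| 0–60 | 11.0 / 13.6 / 17.2 | 13% / 22% / 28% |
| 60–120 | 8.7 / 9.1 / 9.5 | 2% / 5% / 9% |
| 120–180 | 8.6 / 8.7 / 8.8 | 0.1% / 0.7% / 1.7% |

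The distortion fades because a progressed patient's event is restored, at its progression date, once that patient dies.

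**B. Sensible reading.** Documented progression counts. A fraction q stops assessment at a time uniform on 0–12 months. Last contact is at 12–60 months. Deaths count as events whenever they occur. For t ≤ 12:

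S(t) = (1−q)·e^(−λT·t) + q·e^(−λD·t) · [ (1 − e^(−λP·t))/(12λP) + (1 − t/12)·e^(−λP·t) ]

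Example with q = 0.2, OS median 20, t = 9.04: 0.8 × 0.4826 + 0.2 × 0.7310 × (0.6166 + 0.1628) = 0.386 + 0.114 = 0.500, so the median is 9.04 months.

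| q | Median PFS, OS 15 / 20 / 25 | 12-month PFS |
|---|---|---|
| 10% | 8.75 / 8.81 / 8.85 | 39% / 39% / 40% |
| 20% | 8.91 / 9.04 / 9.13 | 40% / 41% / 41% |
| 30% | 9.08 / 9.29 / 9.44 | 41% / 42% / 43% |

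The true values are 8.6 months and 38%.

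**C. Sensitivity to the model.** A second simulation used 5-year uniform accrual, deaths as only 10% of PFS events, and median post-progression survival of 6, 12 or 24 months.

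- Literal rule: medians of 10.6, 14.1 and 31.0 months at a data cut 60 months after accrual starts; 8.6, 8.7 and 9.8 at 120 months; 8.6–8.7 at 240 months.
- Sensible reading, 60-month cut: 9.0 months with 10% unassessed, 9.3–9.7 with 20%, 9.7–10.3 with 30%.

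The direction is the same. The size depends on inputs that the documents do not supply.

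**The case against.** The event definition comes first, and under it a progressed patient's PFS time has already ended, so there is nothing left to censor. Most programmers would work that way. This stands: the first limb is a contradiction to reconcile, and it does not show that the analysis will be run literally.

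A reader might infer that reported PFS will be inflated to 13 months or more. The documents do not support that. The figure needs the literal reading and an early data cut, while follow-up runs up to 15 years and the effect has almost gone by then. The year-5 interim report is the exposed one, if PFS is tabulated in it.

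A reader might also put the second limb at 9.0, 9.6 and 10.2 months for 10%, 20% and 30% unassessed. Those figures treat unassessed patients as event-free until last contact. The protocol counts death from any cause as a PFS event and collects deaths on an event-driven form (section 9.6.5.2). Counting deaths in that model gives the smaller values in part B.

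The share of patients in contact but unassessed is an assumption. Section 9.8 predicts gaps and loss to follow-up, which is not the same thing, and last contact is with the treating site, where disease status may well be known. Finally, censoring at last assessment is unbiased only if patients stop assessment for reasons unrelated to prognosis. These points limit the size of the problem. They do not repair the sentence.

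**Conclusion.** The point holds as a should-fix. As written, the PFS censoring sentence contradicts the event definition before it. On its sensible reading it uses the less suitable of two dates that the study collects. Both effects bias PFS upward.

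Against a true median of 8.6 months, the literal rule gives about 11–17 months at early looks and 8.6–8.8 months with ten or more years of follow-up. The sensible reading, with deaths counted, gives about 8.7–9.4 months for 10–30% unassessed. These figures rest on exponential times, an assumed OS median of 15–25 months and an assumed unassessed share. Other assumptions move them, as part C of the working shows.

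It is tempting to say that a comparison with the pivotal 8.6 months would be compromised, or that the study's conclusions are at risk. The protocol plans no such comparison: section 9.1 rules out comparison groups and inferential testing. PFS is a secondary, descriptive endpoint, and the primary safety conclusions are unaffected.

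**What to change.** Replace the PFS censoring sentence with:

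> Patients alive without documented relapse or progression will be censored at the date of their last disease (effectiveness) assessment, or at the infusion date if there is none; additional treatment is not a reason for censoring.

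Keep last-contact censoring for OS, and report it for PFS as a sensitivity analysis.

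The cost is one sentence and no new data, since Table 4 already holds the date. Some PFS person-time is lost. Censoring at last assessment may itself be informative if patients stop assessment because they are deteriorating, which is why both versions should be shown.

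Deaths after a gap in assessment still count as events at the date of death under this wording. That leaves a small upward residue: a simulation of the part B model gave 8.6–8.8 months, and the second model 8.7–9.2 months with 5–30% unassessed. If deaths after a gap are also censored at the last assessment, the median returns to about 8.6, but only when stopping is random. The SAP can say how such deaths are treated.
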